## **5.4 TREATMENT EXPOSURE AND COMPLIANCE**

In SS, summarize exposure of study treatment.

### **5.4.1 Treatment Exposure**

Summary of treatment exposure includes duration of exposure, number of cycles completed and total dose.

- **Duration of Exposure**

Duration of exposure (days)=last dose date-first dosedate+21.

- **Dosage**

Following variables are summarized descriptively:

- Total dose(mg)=total dose received during the study
- Average dose per cycle(mg) = actual total dose received/(duration of exposure in days /21)

## 5.5 EFFICACY ANALYSIS

Efficacy analyses will be based on FAS and PP. A sensitivity analysis based on all enrolled subjects may also be conducted. The efficacy analysis will be based on Lugano 2014.

### 5.5.1 Primary Analysis

The ORR is defined as the proportion of subjects with CR or PR as Best Overall Response (BOR).

$$ORR = \frac{CR + PR}{\text{Total Number of Subjects}} * 100\%$$

For ORR, the point estimate and 95% confidence interval will be provided using exact binomial distribution.

### 5.5.2 Secondary Analysis

DCR

$$DCR = \frac{CR + PR + SD}{\text{Total Number of Subjects}} * 100\%, \text{ and 95\% CI will be calculated using binomial distribution.}$$

PFS

PFS: the time from the date of the first dose to the date of first disease progression (imaging), if subjects died due to any reason prior to disease progression, PFS is defined as the time from the date of the first dose to the date of death. Subjects who did not die or had disease progressed will be censored on the date of the last imaging assessment date. Subjects with no post-baseline imaging assessment will be censored on the date of the first dose of study medication. Subjects treated with other anti-cancer therapy before PD will be censored at last non-missing tumor assessment date before starting of the new anti-cancer therapy.

Kaplan-Meier method will be used for the analysis of PFS to evaluate the median PFS (mPFS), PFS rate at 6 month and at 1 year, and its 95% CI and the survival curves will be provided accordingly.

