 13. Subjects with positive bone marrow biopsy at baseline shall repeat the biopsy if a CR by imaging is achieved during the treatment (shall be completed within 2 weeks after imaging evaluation).
 14. Tumor biopsy: The investigator may decide whether a biopsy is needed to confirm the results of an imaging evaluation during the study.
 15. CT/MRI evaluation: contrast-enhanced CT will be used (MRI will be performed for subjects allergic to CT contrast media). Contrast-enhanced CT shall be performed at baseline, week 24 (± 7 days), every 12 weeks (± 14 days) after 24 weeks, every 24 weeks (± 14 days) after 48 weeks and when clinical need arises until initiation of new anti-tumor therapy, PD, withdrawal of ICF, or death.

16. PET-CT evaluation: PET-CT shall be performed at baseline, week 6 (± 7 days), week 15 (± 7 days), week 24 (± 7 days) , and when clinical need arises. PET-CT evaluation shall be performed at the end of treatment for subjects who discontinue the treatment prematurely prior to week 24.
17. Disease-related symptom (including fever, night sweats, weight loss) evaluation shall be performed prior to administration in each cycle.
18. IBI308 200mg IV Q3W until PD, death, intolerable toxicity, withdrawal of ICF, or other reasons stated in the protocol. For subjects who develop PD for the first time and are clinically stable, the investigator can continue treatment up to 24 months until further PD, death, intolerable toxicity, withdrawal of ICF, or other reasons stated in the protocol.
19. Quality of life evaluation will be performed on the day of the first dose, during each imaging evaluation, and during the end-of-treatment visit as per EQ 5D-5L and EORTC QLQ-C30.
20. All the eligible subjects must provide archival tumor tissue at baseline or 8–10 unstained sections (4–5 μm) of fresh samples during screening for evaluations of biomarkers. Tests shall be conducted at the central laboratory.
21. Ten mL whole blood samples are required to be provided by subjects for molecular tumor testing at the following time points: prior to the first dose, during efficacy evaluation but before the next treatment, and when PD is confirmed.
22. Treatment discontinuation: treatment discontinuation includes premature discontinuation (treatment discontinuation for reasons other than PD) and end of treatment (treatment discontinuation due to PD). The end-of-treatment visit shall be conducted when treatment is discontinued.

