6.2.6 Survival Follow-Up

After completing the safety follow-up, the subject shall be contacted with (telephone visits is allowed) once 60 days (± 7 days) to obtain the survival information, any subsequent systemic anti-tumor therapy, and PD information (for subjects with no imaging PD). Long-term follow-up shall be continued until death or end of study.

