- Hospitalization or prolonged hospitalization as required by study protocol (such as for dose administration or efficacy evaluation).
- Hospitalization due to a pre-existing medical condition that remains stable, e.g. elective

surgery/therapy scheduled prior to the study.

However, elective surgery/therapy required because of the exacerbated condition during the study (e.g. surgery/therapy required earlier than scheduled) shall be considered as an AE.

PD

PD is defined as the worsening of subject condition caused by the primary tumor that the study drug is targeting, the appearance of new lesions, or the progression of the primary lesion. PD will not be reported as an AE. Any deaths, life-threatening events, hospitalization or prolonged hospitalization, permanent or significant disability/incapacity, congenital anomaly/birth defects, or other important medical events caused by PD will not be reported as an SAE.

Overdose

An overdose is the administration of a drug at more than the dose specified in the study protocol. All the occurrences of overdose must be documented in the eCRF.

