8.4.3 Analysis of secondary efficacy endpoints

- TTR

TTR (CR or PR): time from the first dose to the first tumor response.

The median TTR and corresponding 95% CI will be estimated via the Kaplan-Meier method, and survival curves will be plotted.

- DoR

DoR (CR or PR): time from first date of response to PD or death. Subjects who neither progress nor die will be censored at the date of their last tumor imaging evaluation.

The median DoR and corresponding 95% CI will be estimated via the Kaplan-Meier method, and survival curves will be plotted.

- PFS

PFS: time from first dose to first PD (by imaging), or to death due to any causes. Subjects who neither progress nor die will be censored at the date of their last tumor imaging evaluation. Subjects who did not have any tumor imaging evaluation after baseline will be censored on the date of enrollment.

The median PFS (mPFS) and corresponding 95% CI will be estimated via the Kaplan-Meier method, and survival plots will be plotted.

- OS (investigator-evaluated)

OS: time from first dose to death.

The median OS and corresponding 95% CI will be estimated via the Kaplan-Meier method, and survival curves will be plotted.

- DCR

$$DCR = \frac{\text{Number of Subjects with CR + PR + SD}}{\text{Total Number of Subjects}} * 100 \%$$

, superiority is tested using 95% CI based on the binomial distribution.

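### Progression recorded without a scan is never a PFS event, and SAP 5.5.2 can censor it at an earlier scan, so PFS may be overstated; a sensitivity analysis should be pre-specified

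*SAP*

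**What the plan says.** **PFS event.** Protocol 8.4.3 defines PFS as "time from first dose to first PD (by imaging), or to death due to any causes". SAP 5.5.2 also ties the event to imaging ("the time from the date of the first dose to the date of first disease progression (imaging") and keeps death from any cause before progression as an event, on the day it occurs.

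**PFS censoring.** SAP 5.5.2: "Subjects who did not die or had disease progressed will be censored on the date of the last imaging assessment date". A subject with no post-baseline scan is censored at first dose (protocol 8.4.3 says the enrollment date). A subject given other anti-cancer therapy before PD is censored at the last assessment before it; this rule is in the SAP only.

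**PD elsewhere in the protocol.** The item on investigator decisions in 4.4 covers stopping for PD, or because continuing is judged inappropriate, without mentioning imaging. The adverse event rules (7.5.3) say "PD is defined as the worsening of subject condition caused by the primary tumor that the study drug is targeting", alongside new lesions and progression of the primary lesion. Survival follow-up (6.2.6) records "any subsequent systemic anti-tumor therapy, and PD information (for subjects with no imaging PD").

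**Imaging at treatment stop.** Table 1, note 16: "PET-CT evaluation shall be performed at the end of treatment for subjects who discontinue the treatment prematurely prior to week 24". Note 22 splits stops into "premature discontinuation (treatment discontinuation for reasons other than PD) and end of treatment (treatment discontinuation due to PD"). Section 6.3 continues scheduled imaging after a stop only for subjects who stopped for reasons other than PD.

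**The concern.** The protocol provides for progression that is not documented on imaging and collects information on it, but the PFS definition has no place for it. A subject who worsens between scans, stops with PD as the recorded reason and moves to new therapy leaves the PFS risk set at an earlier scan. That censoring is caused by the progression. Kaplan-Meier assumes that censored subjects have the same outlook as those still at risk, and here they do not. This mechanism can only push the curve upward.

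At stake are the median PFS and the 6-month and 1-year rates. PFS and its 6-month rate are stated secondary objectives. The amendment summary mentions 28 enrolled subjects, so each subject is 1/28 = 3.6 percentage points and a few such cases would show.

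**Working it through.** **1. Following one subject through the rules.** Scans before and at week 24 are due at baseline and weeks 6, 15 and 24 (6.3). Take a subject who worsens at week 10, stops with PD recorded, has no scan and starts new therapy at week 12.
- Note 22 classes the stop as end of treatment, not premature, so the requirement in note 16 does not reach it.
- Section 6.3 does not continue scheduled imaging, because the stop was for PD.
- SAP 5.5.2 censors at the week 6 scan.

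If the worsening and the new therapy come before any post-baseline scan, the subject is censored at first dose and contributes nothing. If the subject dies without new therapy, the death is a PFS event, later than the progression. SAP 4.3 sends missing tumor evaluations to a data review meeting, but only to set the time of censoring; nothing there turns the progression into an event.

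**2. What the documents give for size.** They state no assumed PFS, PFS event count or share of progressions without imaging. The only design calculation is for ORR and does not enter here. There is no figure to reproduce, so the size is explored under assumptions.

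**3. Simulation.**
- From the protocol: scans at weeks 6, 15 and 24, then every 12 weeks to week 48, then every 24 weeks (36, 48, 72, 96).
- Assumed: exponential progression times with median 3, 6 or 9 months; 10%, 20% or 30% of progressions clinical only, with no triggered scan; 0% to 100% of those subjects dying without new therapy, with median survival of 3 months after progression; 200,000 subjects per setting.
- Imaging PD is dated at the next scheduled scan. Under the SAP rule a clinical-only progression is censored at the last scan before it, unless the subject dies without new therapy (event at death). In the comparator it is an event on its own date.

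6-month PFS (the SAP column runs from all such subjects dying without new therapy to none):

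| True median | Clinical-only share | Counted as event | SAP rule | Difference (points) |
|---|---|---|---|---|
| 3 months | 10% | 27.6% | 31.0-31.1% | 3.4-3.5 |
| 3 months | 20% | 27.3% | 34.3-34.6% | 7.0-7.3 |
| 3 months | 30% | 27.0% | 37.5-38.8% | 10.5-11.8 |
| 6 months | 10% | 52.5% | 55.0-55.9% | 2.5-3.4 |
| 6 months | 20% | 52.2% | 57.1-59.3% | 4.9-7.1 |
| 6 months | 30% | 51.9% | 59.5-63.0% | 7.6-11.1 |
| 9 months | 10% | 65.2% | 67.0-68.1% | 1.8-2.9 |
| 9 months | 20% | 64.9% | 68.7-70.8% | 3.8-5.9 |
| 9 months | 30% | 64.7% | 70.4-73.8% | 5.7-9.1 |

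In the 3-month, 10% row the two ends are equal within simulation error. With no clinical-only progression the two analyses agree exactly. At a 6-month median, a 20% share and new therapy for all such subjects, the 1-year rate rises from about 27% to 35%. The median moves in jumps because of the scan grid: in many settings not at all, at most by about 5.7 months.

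**4. Scale.** With 28 subjects and a 6-month median, 14 progress by month 6. Shares of 10%, 20% and 30% are then 1.4, 2.8 and 4.2 subjects. The standard error of a 6-month rate near 52%, ignoring censoring, is √(0.522 × 0.478 / 28) = 9.4 points. The 20% case (4.9 to 7.1 points) is about 0.5 to 0.75 of that.

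**The case against.** **Scans can be triggered.** Notes 15 and 16 provide for CT and PET-CT on clinical need, and 6.3 adds unplanned scans at the sponsor's expense if the subject agrees. A subject worsening between visits is the obvious case. This stands: the simulated figures assume no such scan and shrink as triggered scans capture progressions.

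**A reader might infer that the protocol exempts these subjects from the end-of-treatment PET-CT.** It does not say so. The gap comes from reading notes 16 and 22 together, and it depends on the site recording PD as the reason. A stop recorded as investigator judgement counts as premature: PET-CT applies before week 24, unless one was done in the past month, and imaging continues. Table 1 also marks PET-CT in the combined end-of-treatment column, and 6.2.4 lists it where applicable.

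**A reader might infer that first PD may be declared clinically.** No section says this outright; it is inferred from 4.4, 6.2.6 and 7.5.3, and 7.5.3 serves adverse event reporting. Section 3.2.5 refers to initial PD by Lugano 2014, and 6.3 asks for first PD to be confirmed. The one explicit stop for clinical worsening without imaging (5.1.2) applies after initial PD, when an imaging PD has already counted.

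**A reader might infer from the early PDs in the amendment summary that this path is common.** That text concerns pseudo-progression under Lugano 2014, with treatment continued. It is not evidence of stops without a scan.

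**A reader might extend the point unchanged to DoR.** Neither DoR definition restricts progression to imaging, and neither has a new-therapy rule. The problem there is ambiguity: the event is progression, but censoring is at the last imaging assessment.

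**Imaging-only PFS is a defensible choice** in an open-label trial, because clinical progression dates are subjective. This stands, and it is the reason to add an analysis beside the planned one and not to replace it.

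**Conclusion.** The concern holds in a limited form. PFS events are imaging PD or death, progression recorded without imaging is collected but unused, and such subjects who are alive or given new therapy are informatively censored. PFS and its 6-month and 1-year rates may therefore be overstated.

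The documents do not support saying that PFS is overstated. The frequency is unknown, death remains an event, triggered scans help, and pseudo-progression on imaging counts as an event and pulls PFS down. The net bias cannot be determined.

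For this mechanism alone, under the assumed exponential times and with no triggered scans, 6-month PFS is about 2-4 points too high if 10% of progressions are clinical only, 4-7 at 20% and 6-12 at 30%. Except at the upper end, this is below the standard error at 28 subjects. The primary ORR conclusion does not depend on it.

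**What to change.** - **SAP 5.5.2, PFS.** Keep the imaging-only analysis. Pre-specify a sensitivity analysis that counts treatment end recorded as PD, or PD reported at survival follow-up without imaging, as an event at that date, including when new therapy follows. Report it beside the planned result.
- **DoR (SAP 5.5.2, protocol 8.4.3).** State whether PD without imaging counts, and run the same sensitivity analysis.
- **Consistency.** Reconcile the no-scan censoring date (enrollment in protocol 8.4.3, first dose in SAP 5.5.2). Reconcile notes 16 and 22, section 6.2.4 and section 6.3 on who receives the end-of-treatment PET-CT. No scan rule is proposed here.

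The cost is one extra set of PFS and DoR estimates. The inputs are already called for: protocol 4.4 requires reasons and dates of discontinuation, and 6.2.6 collects the follow-up PD information. The drawbacks are subjective event dates in an open-label trial and, if such subjects exist, a slightly less favourable PFS.

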6.3 Imaging Evaluation

Baseline evaluation is conducted within 28 days prior to the first dose of the study treatment. The investigator can evaluate the imaging results within 28 days prior to the enrollment.

PET-CT and contrast-enhanced CT will be used (MRI will be performed for subjects allergic to CT contrast media). PET-CT shall be performed at baseline, week 6 (± 7 days), week 15 (± 7 days), and week 24 (± 7 days). PET-CT evaluation shall be performed at the end of treatment for subjects who discontinue the treatment prematurely prior to week 24 (unless the previous PET-CT scan is done within the past month). Contrast-enhanced CT shall be performed at baseline, week 24 (± 7 days), every 12 weeks (± 14 days) after 24 weeks, and every 24 weeks (± 14 days) after 48 weeks initiation of new anti-tumor therapy, PD, withdrawal of ICF, or death. Unplanned PET-CT and contrast-enhanced CT shall be added to evaluate the efficacy when investigators deem appropriate, if the subjects agree. The examinations will be taken at sponsor's expense. First PD shall be confirmed after 4–6 weeks. For subject who discontinue the treatment for reasons other

than PD, tumor imaging evaluation shall be continued according to the study protocol until initiation of new anti-tumor therapy, PD, withdrawal of ICF, or death.

Imaging data shall be copied or saved according to the requirements of the sponsor.

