8.5 Sample size estimation

This is a single-arm trial. The primary objective is to evaluate the efficacy of IBI308 monotherapy for the treatment of relapsed or refractory extranodal NK/T-Cell Lymphoma. 20-60 subjects will be enrolled. Assuming a null hypothesis of 30% ORR, α of 0.05 (two-sided), power of 80%, a 50% ORR after IBI308 treatment will be achieved and the minimum sample size will thus be 43.

The sponsor will evaluate the safety data from the first 20 subjects to determine whether the study shall be discontinued prematurely due to safety concerns.

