## STATISTICAL ANALYSIS PLAN

Innovent Biologics (Suzhou) Ltd  
Protocol number: CIBI308D201

Version: 2.0  
Version Date: 2020-02-28

---

- if month and date are missing, it will be assumed as July 1st with no conflict with other date variables;
- if dates are missing, it will be assumed as 15th with no conflict with other date variables;
- Original date collected from CRF will be shown in the listings.
- Missing data handling of other variables

Efficacy variables: All missing in the primary efficacy endpoints due to early withdrawal or lost follow up will be treated as "unable to evaluate ". In the calculation of time to event variables (e.g. PFS, DOR), subjects who have tumor evaluation missing after treatment will be reviewed to determine the time of censoring during data review meeting prior to database lock.

There will be no missing value imputation for baseline and safety data.

The extreme value of laboratory data identified as being caused by improper handling of specimens and blood samples will be replaced by unplanned visit data in the visit window (if available) as defined by the protocol. If these values cannot be replaced, they will be set as missing and be excluded from the analyses.

- Definition of baseline

The last non-missing data before first study drug administration will be defined as the baseline.

- Data derivation rules

Age (year) = (Informed Consent Date of Signature – Birth Date +1)/365.25, round to 1 decimal digits;

Course of first diagnosis (Day) = Informed Consent Date of Signature – Birth Date +1;

For efficacy related data derivation, see the sections which define efficacy endpoints.

- **Missing Relationship of AE to Study Treatment**

If relationship is missing, no imputation is made but will be considered as related.

- **Missing CTCAE grade**

Missing grade will not be imputed but will be counted in summary as grade  $\geq 3$  and will be listed separately.

- **Handling of Outliners**

NA

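### The PFS rules conflict for a subject who dies before any post-baseline scan: the definition makes the death an event, the no-imaging sentence censors it

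*SAP*

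**What the plan says.** The PFS paragraph of SAP 5.5.2 gives these rules, in this order:

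- **Event.** Progression on imaging is an event. So is death: "if subjects died due to any reason prior to disease progression, PFS is defined as the time" from first dose to death. No scan is required.
- **General censoring.** "Subjects who did not die or had disease progressed will be censored on the date of the last imaging assessment date". The wording is garbled, but it is evidently meant for subjects with neither event.
- **No imaging.** "Subjects with no post-baseline imaging assessment will be censored on the date of the first dose of study medication". There is no condition on survival.
- **New therapy.** Subjects given another anti-cancer therapy before progression are censored at the last assessment before it started.

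Protocol 8.4.3 is built the same way. PFS runs from first dose to first progression "or to death due to any causes". Subjects with neither event are censored at the last imaging date. Then: "Subjects who did not have any tumor imaging evaluation after baseline will be censored on the date of enrollment". The censoring date therefore differs between the documents (enrollment against first dose), but the missing condition is common to both.

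SAP 4.3 adds that, for time-to-event variables, "subjects who have tumor evaluation missing after treatment will be reviewed to determine the time of censoring during data review meeting prior to database lock". It does not mention deaths.

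**The concern.** A subject who dies before the first post-baseline scan meets both the event definition and the no-imaging condition. One makes the death an event on its date; the other removes the subject from the risk set at the start. Neither document ranks the two.

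The situation can arise. In Protocol 6.3, "PET-CT shall be performed at baseline, week 6" and then weeks 15 and 24, so the first scheduled post-baseline scan comes about six weeks after first dose. Protocol 1.1 describes prognosis after failure of L-asparaginase-based regimens as extremely poor.

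Censoring these deaths would be informative, because the subjects removed are those with the worst outcome. PFS and 6-month PFS are named secondary objectives, and the SAP also reports the median and the 1-year rate. All of these could be affected.

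**Working it through.** **1. The text, for one subject.** Take a subject who is dosed, has no post-baseline scan and dies in week 4.

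- Event definition (SAP 5.5.2, Protocol 8.4.3): event in week 4.
- General censoring sentence: does not apply, since the subject died.
- No-imaging sentence: applies as worded. Censored at first dose (SAP) or enrollment (protocol).
- SAP 4.3: sends the case to a data review meeting to fix a censoring time, without saying whether a death should be censored at all.

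The authors do state the restriction elsewhere: in the general PFS censoring sentence, and in the SAP's DOR rule, which censors only subjects without progression or death. The no-imaging sentence lacks it.

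**2. The plan's own figure.** The documents state no PFS figure to reproduce. The one design figure is 43 subjects for ORR: "Assuming a null hypothesis of 30% ORR", against 50%, two-sided 0.05, 80% power. The normal approximation gives

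n = [(1.960 × √(0.30 × 0.70) + 0.842 × √(0.50 × 0.50)) / 0.20]² = 43.49,

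which rounds up to 44, with power of 79.6% at 43. That agrees with the plan to within one subject. PFS does not enter the formula.

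**3. Inputs for the illustration.**

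- n = 28: the number enrolled according to the protocol's Summary of Amendment. Used for illustration only.
- k, deaths before any post-baseline scan: not in the documents; assumed 1 to 5.
- True 6-month PFS: not in the documents; assumed 40%.
- No other censoring before 6 months: assumed.

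**4. Formula.** Let m be the number event-free at 6 months.

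- Deaths counted as events: S = m / n.
- Deaths censored at the start: S = m / (n − k).
- So reported S = true S × n / (n − k). The factor exceeds 1 whenever k is at least 1.

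**5. Results at n = 28, true S = 40%.**

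| k | Calculation | Reported 6-month PFS | Overstatement (points) |
|---|---|---|---|
| 1 | 0.40 × 28/27 | 41.5% | 1.5 |
| 2 | 0.40 × 28/26 | 43.1% | 3.1 |
| 3 | 0.40 × 28/25 | 44.8% | 4.8 |
| 4 | 0.40 × 28/24 | 46.7% | 6.7 |
| 5 | 0.40 × 28/23 | 48.7% | 8.7 |

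**6. Sensitivity to the assumptions.** Now fix s, the 6-month PFS among the other n − k subjects. Counting the deaths as events gives s × (n − k)/n; censoring them gives s.

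- n = 28, s = 50%: 48.2%, 46.4%, 44.6%, 42.9% and 41.1% for k = 1 to 5, against 50% if censored. The overstatement is 1.8 to 8.9 points.
- n = 28, s from 40% to 60%: 1.4 to 2.1 points at k = 1, and 7.1 to 10.7 points at k = 5.
- n = 43, s = 50%: 1.2 points at k = 1, and 5.8 points at k = 5.

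**The case against.** The strongest reply is that the paragraph should be read in sequence. It defines the events, then censors subjects without an event at their last scan, then deals with subjects who have no scan to be censored at. On that reading the third sentence only fills a gap in the second, and an early death is an event throughout. The protocol's cleaner wording of the general rule supports this, and it is the more natural reading.

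A reader might therefore go too far in saying that the plan censors early deaths at day 1. The documents do not support that. Nowhere do they say that such a death is to be censored, and the event definition says the opposite. Nor do they show which rule a programmer would follow. The no-imaging sentence is not even the last one in the SAP paragraph.

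A reader might also infer that unscanned deaths are to be expected. That is not shown either. Eligibility requires a life expectancy of at least 12 weeks, twice the time to the first scheduled scan. Protocol 6.3 allows unscheduled scans and asks for a PET-CT at end of treatment for those stopping before week 24. No count of such deaths is given. These points make the deaths fewer, but cannot rule them out.

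What the reply does not do is secure its own reading. The new-therapy sentence in the same SAP paragraph censors subjects with no exemption for a later progression or death, so censoring sentences there do not always yield to events. SAP 4.3 leaves the matter to a meeting, in an open-label single-arm trial where outcomes are visible.

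It is also true that the reach is limited. PFS is a secondary endpoint reported by estimation, and OS and the listing of deaths still capture every early death.

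**Conclusion.** The point holds as a conflict between two instructions, present in both documents and not resolved by SAP 4.3. It is not a demonstrated error in a settled rule. If the no-imaging sentence is applied as written, the 6-month PFS estimate is biased upward and the median can only move in the drug's favor. On the main assumptions the bias is 3.1 points for two such deaths and 6.7 points for four. These figures rest on an assumed true 6-month PFS, an assumed number of deaths and no other censoring before 6 months. If no subject dies unscanned, the bias is zero. The primary ORR analysis and the sample size of 43 do not depend on it. The wording should be corrected, because it affects a named secondary endpoint and the correction is small.

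**What to change.** In SAP 5.5.2, replace the no-imaging sentence with wording such as: *A subject who did not die and has no post-baseline imaging is censored on the date of first dose. A death without post-baseline imaging is a PFS event on the date of death.*

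Align Protocol 8.4.3 at the next amendment, both by adding the same condition and by settling the censoring date. PFS is timed from first dose in both documents, so first dose is the consistent choice; enrollment may precede the start of the PFS clock.

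The SAP change is a few words. The protocol change goes through the amendment process in Protocol 11.3, which is why it can wait for the next one. If the sponsor already intends to count these deaths, no result changes. Otherwise reported PFS may be slightly lower.
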